## 5.3 **Dose Level Schema**

### 5.3.1 **Uproleselan (GMI-1271) Dosing:**

The starting dose will be 10 mg/kg with dose levels for subsequent groups of patients as follows.

**Table 5 – Uproleselan Dose Level Schema**

Dose Level	Uproleselan (GMI-1271) dose
-1	5 mg/kg
1*	10 mg/kg

\*Starting dose level

A Dose Level 2 will only be considered after evaluation of PK and toxicity at Dose Level 1. If PK clearance is >30% compared to adults and if the MTD has not been reached at Dose Level 1, a Dose Level 2 will be considered.

If the MTD has been exceeded at the first dose level, then the subsequent cohort of patients will be treated at Dose Level -1. If Dose Level -1 is not well tolerated, further de-escalation will not occur. The study will be closed to accrual.

#### 5.4 Grading of Adverse Events

Adverse events (toxicities) will be graded according to the NCI Common Terminology Criteria for Adverse Events (CTCAE) version 5.0. All appropriate treatment areas should have access to a copy of the CTCAE version 5.0. A copy of the CTCAE version 5.0 can be downloaded from the CTEP website ([https://ctep.cancer.gov/protocolDevelopment/electronic\\_applications/ctc.htm](https://ctep.cancer.gov/protocolDevelopment/electronic_applications/ctc.htm)). Any suspected or confirmed dose-limiting toxicity should be reported immediately (within 24 hours) to the Study Chair. For laboratory values in CTCAE with grading definitions including both baseline and ULN definitions, utilize the ULN for CTCAE grading.

#### 5.5 Definition of Dose-Limiting Toxicity (DLT)

DLT will be defined as any of the following events that are possibly, probably or definitely attributable to protocol therapy. The DLT observation period will be the first cycle of therapy. Please refer to [Section 13.5.4](#) for AE resolution definitions

Dose limiting hematological and non-hematological toxicities are defined differently.

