## 5.0 TREATMENT PLAN

### 5.1 Overview of Treatment Plan

**Table 2 – Experimental Design Schema**

Each Cycle (28 days)						
	Uproleselan (GMI-1271) IV	Fludarabine IV	Cytarabine IV	Cytarabine IT	IT Triples	Leucovorin PO or IV
Day 0				once daily 	once daily 	
Day 1	once daily					24 and 30hrs post ITT 
Day 2	q12hr	once daily	once daily			
Day 3	q12hr	once daily	once daily			
Day 4	q12hr	once daily	once daily			
Day 5	q12hr	once daily	once daily			
Day 6	q12hr	once daily	once daily			
Day 7	q12hr			Weekly 	Weekly 	
Day 8	q12hr					24 and 30hrs post ITT 
Day 9						
...						
Day 14				Weekly 	Weekly 	
Day 15						24 and 30hrs post ITT 
Day 21				Weekly 	Weekly 	
Day 22						24 and 30hrs post ITT 
Day 28				Weekly 	Weekly 	
Day 29 						24 and 30hrs post ITT 

 Choice between IT Cytarabine OR IT Triples is up to the treating physician's discretion. Weekly intrathecal chemotherapy treatments are for CNS 2/3 patients ONLY. A minimum of 4 and a maximum of 6 intrathecal treatments may be given (count includes day 0 IT and may carry over into Cycle 2 of chemotherapy).

 Down syndrome patients ONLY. Administer 24 & 30 hours after each IT Triples.

 End of cycle bone marrow for disease assessment may be performed any day between Day 28-35.

 Day 28 lumbar puncture can be done at the same time as the end of cycle bone marrow assessment between day 28-35.

A cycle of therapy is considered to be 28 days. A cycle may be repeated for a total of 2 cycles, up to a total duration of therapy of approximately 2 months.

Drug doses of uproleselan (GMI-1271) should be adjusted based on the weight measured within 7 days prior to the beginning of each cycle. Drug doses of fludarabine and cytarabine should be adjusted based on the BSA (calculated from the height and weight) or weight (patients < 1 year) measured within 7 days prior to the beginning of each cycle. Drug doses of intrathecal cytarabine, methotrexate and hydrocortisone should be based on the age of the patient at the time of administration.

THIS PROTOCOL IS FOR RESEARCH PURPOSES ONLY, SEE PAGE 1 FOR USAGE POLICY

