##### 5.5.1 Non-hematological dose-limiting toxicity

5.5.1.1 Any Grade 3 or greater non-hematological toxicity attributable to protocol therapy with the specific exclusion of:

- Grade 3 tumor lysis syndrome
- Grade 3 nausea and vomiting < 3 days duration
- Grade 3 liver enzyme elevation, including ALT/AST/GGT, that returns to Grade  $\leq 1$  prior to the time for the next treatment cycle. See [Appendix III](#) for liver function grading parameters in children and adolescents
- Grade 3 fever
- Grade 3 infection
- Grade 3 hypophosphatemia, hypokalemia, hypocalcemia or hypomagnesemia responsive to supplementation.
- Grade 3 sepsis
- Grade 3 rash
- Grade 3 mucositis

5.5.1.2 Non-hematological toxicity that causes a delay of  $\geq 14$  days between treatment cycles.

**Note:** Allergic reactions that necessitate discontinuation of study drug will not be considered a dose-limiting toxicity.

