## 5.5.2 Hematological dose limiting toxicity

### 5.5.2.1 **In patients evaluable for hematological toxicity (see [Section 11.2.1](#)), hematological dose limiting toxicity is defined as:**

Failure to recover a peripheral ANC > 200/ $\mu$ L and non-transfusion dependent platelets > 20,000/ $\mu$ L by 43 days after the first treatment day with fludarabine and cytarabine, not due to malignant infiltration (including MRD by central flow cytometry analysis) or  $\geq$ Grade 3 infection or sepsis. Failure to recover peripheral counts due to disease involvement of the bone marrow will not be considered dose-limiting.

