### 6.1 Dose Modifications for Hematological Toxicity

6.1.1 Patients who experience a hematologic dose limiting toxicity defined as failure to recover a peripheral blood ANC > 200/ $\mu$ L and non-transfusion dependent platelet count > 20,000/ $\mu$ L by 43 days after the start of the cycle, not due to malignant infiltration or severe infection will be allowed to proceed to Cycle 2 at the next lower dose level at the discretion of the treating physician and study chair or vice-chair. If patient is starting at Dose Level -1, further de-escalation will not occur and the patient must be removed from protocol therapy.

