### 10.2 Off Study Criteria

- a) Thirty days after the last dose of the investigational agent
- b) Withdrawal of consent for any required observations or data submission.
- c) The patient does not receive protocol treatment after study enrollment.
- d) Patient enrollment onto another COG study with therapeutic (anti-cancer) intent.
- e) Lost to follow-up
- f) Death

THIS PROTOCOL IS FOR RESEARCH PURPOSES ONLY, SEE PAGE 1 FOR USAGE POLICY

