### **COG Response Criteria:**

#### **COG Complete Remission (COG-CR):**

Attainment of < 5% leukemic blasts in the bone marrow as determined by central flow cytometry with no evidence of circulating leukemic blasts or extramedullary disease and with recovery of peripheral blood counts (ANC ≥ 500/μL and platelet count ≥ 50,000/μL). The qualifying CBC must be drawn on the day of the marrow or up to 7 days after bone marrow. There is no requirement for bone marrow cellularity.

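### The 28-day DLT window ends before two of the protocol's own DLT criteria can be assessed, and the off-study rule can end follow-up before one of them

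*Combined protocol and SAP*

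**What the plan says.** **Window.** Section 5.5: "The DLT observation period will be the first cycle of therapy". Section 5.1: "A cycle of therapy is considered to be 28 days". The MTD definition (11.2.2) and the dose rule (11.3) both count DLTs in Cycle 1. Under 11.3, two or more at DL1 among up to six evaluable patients means the MTD has been exceeded.

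**Criteria that mature late.** Section 5.5.2.1 makes failure to recover both counts a DLT when it persists "by 43 days after the first treatment day with fludarabine and cytarabine". Section 5.5.1.2 adds "Non-hematological toxicity that causes a delay of" 14 days or more between cycles.

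**A second anchor.** Section 6.1.1 describes the same hematological event as non-recovery "by 43 days after the start of the cycle". Section 6.2.3 uses that anchor too, for resolution of non-hematological toxicity.

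**End of follow-up.** Section 10.1 follows patients who are off protocol therapy until they meet an off-study criterion, and 10.2(a) is "Thirty days after the last dose of the investigational agent". Section 10.1 extends observation to adverse-event resolution, if later than the planned end of cycle, only for patients removed during Cycle 1.

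**Response.** Section 5.6 allows the end-of-cycle marrow on Days 28 to 35. Appendix VIII says: "The qualifying CBC must be drawn on the day of the marrow or up to 7 days after bone marrow".

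**The concern.** A window that closes on Day 28 cannot contain an event that is established on Day 43 or Day 45, and no sentence extends the window for either criterion. If the study team scores a patient DLT-free at the end of a 28-day cycle, prolonged cytopenia and toxicity-related delay drop out of the count that answers primary aim 1.1.1. With a threshold of two patients in six, one misclassified patient can decide whether DL1 becomes the RP2D and Part B opens, or DL-1 opens instead.

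The off-study rule raises a separate data problem. A patient can leave follow-up before the count that decides the hematological DLT is due, and after Cycle 2 before the last blood count that could qualify a response.

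**Working it through.** **Inputs**
- Cycle length 28 days (5.1).
- First fludarabine/cytarabine day: Day 2 (5.1.2, 5.1.3).
- Uproleselan once on Day 1 and twice daily on Days 2 to 8. This gives 1 + 7 × 2 = 15 doses, which reproduces the total in 5.1.1, so the last planned dose is on Day 8.
- Cycle 2 taken as due on Day 29 (5.2 repeats cycles every 28 days).

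**Calendar, dosing on schedule**

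| Event | Arithmetic | Day | Days after Day 28 |
|---|---|---|---|
| Window closes, read literally | 28 | 28 | 0 |
| Off study under 10.2(a), therapy stopped after Cycle 1 | 8 + 30 | 38 | 10 |
| Last permitted response CBC | 35 + 7 | 42 | 14 |
| Delay DLT (5.5.1.2) | 29 + 14 | 43 | 15 |
| Hematological event (6.1.1 anchor) | 1 + 43 | 44 | 16 |
| Hematological DLT (5.5.2.1) | 2 + 43 | 45 | 17 |

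Off study on Day 38 comes 7 days before the 5.5.2.1 assessment (45 − 38) and 6 days before the 6.1.1 date (44 − 38). After Cycle 2, on that cycle's own day count, it comes 4 days before the last permitted response CBC (42 − 38).

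**Effect on the dose rule.** The documents give no DLT rates, so the rates below are assumptions. For six evaluable patients, each with probability p of a DLT:

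P(at least 2) = 1 − (1 − p)^6 − 6p(1 − p)^5

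Hematological DLTs alone:
- p = 0.05: 1 − 0.735 − 0.232 = 0.033
- p = 0.10: 1 − 0.531 − 0.354 = 0.114
- p = 0.20: 1 − 0.262 − 0.393 = 0.345
- p = 0.30: 1 − 0.118 − 0.303 = 0.580

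Now add an assumed 10% rate of non-hematological DLTs seen inside 28 days, independent of the hematological ones, so that p = 1 − 0.90 × (1 − h), where h is the hematological rate:

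| h | p | Chance rule triggers, late events counted | Not counted |
|---|---|---|---|
| 5% | 0.145 | 21.2% | 11.4% |
| 10% | 0.190 | 32.0% | 11.4% |
| 20% | 0.280 | 53.6% | 11.4% |
| 30% | 0.370 | 71.7% | 11.4% |

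**Sample size.** The expected maximum of 22 in 11.1 reproduces as (6 + 6 + 6) × 1.2 = 21.6, rounded up. It does not depend on the length of the window.

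**The case against.** The strongest reply is that the plan clearly means to count these events. The 43-day limit sits inside the DLT definition, and Section 5.5 says that hematological and non-hematological DLTs are defined differently. Section 6.1.1 treats non-recovery at 43 days as a recognised DLT in a patient who has not yet started Cycle 2. The 28 days are nominal: the schema runs to Day 29, allows the marrow up to Day 35, and gives Cycle 2 on count recovery. No sentence scores anyone DLT-free on Day 28, and the study chair's DLT evaluations are reviewed weekly (14.5.2). This stands as evidence of intent. A reader might infer that the rule cannot count hematological DLTs, or that the chance of triggering it is zero. The documents do not support that: the text is contradictory, and most non-hematological DLTs fall within 28 days and are counted on any reading.

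A reader might also infer that every patient leaves the study on Day 38. That fails too. Section 10.1 applies the off-study criteria to patients already off protocol therapy, and 6.1.1 lets a patient proceed to Cycle 2 after 43 days without recovery. Table 8 continues blood counts after Grade 4 cytopenia until Grade 3 or lower with no stop day, and 10.1 requires ongoing adverse events to be followed. What remains is a narrower group: patients who complete Cycle 1 and then leave therapy with counts unrecovered. The explicit extension in 10.1 does not name them, and 10.2(a) can close their follow-up first.

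Finally, the documents do not suggest that high DLT rates are expected. Section 2.5.2 considers it unlikely that DLTs will determine the RP2D, and 5.5.2.1 excludes non-recovery due to disease or to Grade 3 or higher infection. The 20% and 30% rows are therefore illustrations. Response is a secondary, descriptive aim, and a response CBC is lost only if recovery falls on about Days 39 to 42 in a patient already off therapy.

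**Conclusion.** The inconsistency is real and bears on the primary decision. The stated window ends 15 days before the delay criterion and 17 days before the hematological criterion can be assessed, and the hematological event carries two dates one day apart. The likely harm is uneven under-counting of late DLTs, depending on how the window is read. The follow-up gap is 7 days and affects only patients who stop after completing Cycle 1 with counts unrecovered; after Cycle 2 it is up to 4 days for the response CBC.

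The effect on the rule depends on unknown rates: about 3% to 58% for hematological rates of 5% to 30%, taken alone. With a 10% in-window non-hematological rate, leaving late events out lowers the chance of triggering by about 10 to 60 percentage points (21.2 − 11.4 = 9.8; 71.7 − 11.4 = 60.3). These figures assume six evaluable patients, independent events, and either all or none of the late events counted. They bound the effect and do not predict it.

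**What to change.** Reconcile Sections 5.1, 5.5 to 5.5.2, 6.1 to 6.2, 10.1 to 10.2 and 11.2 to 11.3 so that:

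1. The DLT observation period for the MTD/RP2D count runs until every DLT defined for Cycle 1 therapy can be assessed, including count recovery and the between-cycle delay. No patient is scored DLT-free earlier. Count recovery alone should not close the window, because the delay criterion may still be open.
2. The sponsor resolves the anchor conflict between 5.5.2.1 and 6.1.1/6.2.3. These sections also govern dose reduction and removal from therapy, so the choice of day is the sponsor's.
3. Criterion 10.2(a) does not take effect before the required DLT count assessment or, for response, the last qualifying CBC.

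In the same edit, Section 11.2.1 should define hematological evaluability, because 5.5.2.1 refers to it for that and it gives no such definition.

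The cost is protocol wording, up to about 17 more days (45 − 28) before a patient is scored, and a short extension of follow-up for the few patients affected. The planned sample size does not change.

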##### 5.5.1 Non-hematological dose-limiting toxicity

5.5.1.1 Any Grade 3 or greater non-hematological toxicity attributable to protocol therapy with the specific exclusion of:

- Grade 3 tumor lysis syndrome
- Grade 3 nausea and vomiting < 3 days duration
- Grade 3 liver enzyme elevation, including ALT/AST/GGT, that returns to Grade  $\leq 1$  prior to the time for the next treatment cycle. See [Appendix III](#) for liver function grading parameters in children and adolescents
- Grade 3 fever
- Grade 3 infection
- Grade 3 hypophosphatemia, hypokalemia, hypocalcemia or hypomagnesemia responsive to supplementation.
- Grade 3 sepsis
- Grade 3 rash
- Grade 3 mucositis

5.5.1.2 Non-hematological toxicity that causes a delay of  $\geq 14$  days between treatment cycles.

**Note:** Allergic reactions that necessitate discontinuation of study drug will not be considered a dose-limiting toxicity.

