
## EXPERIMENTAL DESIGN SCHEMA

**Table 1 – Experimental Design Schema**

Each Cycle (28 days)						
	Uproleselan (GMI-1271) IV	Fludarabine IV	Cytarabine IV	Cytarabine IT	IT Triples	Leucovorin PO or IV
Day 0				once daily 	once daily 	
Day 1	once daily					24 and 30hrs post ITT 
Day 2	q12hr	once daily	once daily			
Day 3	q12hr	once daily	once daily			
Day 4	q12hr	once daily	once daily			
Day 5	q12hr	once daily	once daily			
Day 6	q12hr	once daily	once daily			
Day 7	q12hr			Weekly 	Weekly 	
Day 8	q12hr					24 and 30hrs post ITT 
Day 9						
...						
Day 14				Weekly 	Weekly 	
Day 15						24 and 30hrs post ITT 
Day 21				Weekly 	Weekly 	
Day 22						24 and 30hrs post ITT 
Day 28				Weekly 	Weekly 	
Day 29 						24 and 30hrs post ITT 

 Choice between IT Cytarabine OR IT Triples is up to the treating physician's discretion. Weekly intrathecal chemotherapy treatments are for CNS 2/3 patients ONLY. A minimum of 4 and a maximum of 6 intrathecal treatments may be given (count includes day 0 IT and may carry over into Cycle 2 of chemotherapy).

 Down syndrome patients ONLY. Administer 24 & 30 hours after each IT Triples.

 End of cycle bone marrow for disease assessment may be performed any day between Day 28-35.

 Day 28 lumbar puncture can be done at the same time as the end of cycle bone marrow assessment between day 28-35.

A cycle of therapy is considered to be 28 days. Upon count recovery, patients may receive a second cycle of uproleselan (GMI-1271) in combination with fludarabine and cytarabine if there is evidence of clinical benefit in the opinion of the treating physician and eligibility criteria are met for organ function criteria.

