### 5.5.2.2 **Note:** Grade 3 or 4 febrile neutropenia will not be considered a dose-limiting toxicity.

## 5.6: THERAPY DELIVERY MAPS (TDMS) FOR CYCLE 1-2

**Therapy Delivery Map – Cycle 1-2** A cycle of therapy is considered to be 28 days. A cycle may be repeated for a total of 2 cycles, up to a total duration of therapy of approximately 2 months. Refer to [section 4.1](#) for eligibility criteria to start cycle 1. For patients in MRD negative remission, it is required that patients have an ANC >200/ $\mu$ L or a sustained platelet count >20,000/ $\mu$ L before proceeding with cycle 2.

This form is to be completed and uploaded into RAVE at the end of every cycle.

Accession #

Patient COG ID number

Institution

Extensive details are in [Section 5.1](#) (treatment overview). This TDM extends to three pages.

DRUG	ROUTE	DOSAGE	DAYS	IMPORTANT NOTES																				
IT Cytarabine (AraC)	Intrathecal (IT)	Age-based dosing: 

Age	Dose	

< 1 year	20 mg	

≥ 1 to < 2 years	30 mg	

≥ 2 to < 3 years	50 mg	

≥ 3 years	70 mg	

	Age	Dose	< 1 year	20 mg	≥ 1 to < 2 years	30 mg	≥ 2 to < 3 years	50 mg	≥ 3 years	70 mg	Days 0 ^ , 7*, 14*, 21*, 28 ^	
^All patients. First time point given at the time of diagnostic lumbar puncture OR Day 0 for all patients. Note that Day 28 LP with IT chemotherapy of Cycle 1 counts as Day 0 LP with IT of Cycle 2. If the patient received IT cytarabine or triple IT therapy during their diagnostic workup within 14 days of starting protocol therapy, then they do not need additional Day 0 IT therapy.
 
*CNS 2/3 patients ONLY.
 
A minimum of 4 and a maximum of 6 weekly (count includes day 0 IT) intrathecal treatments may be given. The choice between IT Cytarabine OR IT Triples is up to the treating physician's discretion. See Section 5.1 for administration guidelines.
										
Age	Dose																							
< 1 year	20 mg																							
≥ 1 to < 2 years	30 mg																							
≥ 2 to < 3 years	50 mg																							
≥ 3 years	70 mg																							

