### 6.2 Dose Modifications for Non-Hematological Toxicity

6.2.1 Patients who have any dose-limiting non-hematological toxicity (as defined in [Section 5.5.1](#)) may continue on protocol therapy upon meeting eligibility lab requirements (see [Section 4.0](#)) or Grade  $\leq 2$  but should receive subsequent doses at the next lower dose level. If patient is starting at Dose Level -1, further de-escalation will not occur and the patient must be removed from protocol therapy.

6.2.2 If a non-hematological dose-limiting toxicity recurs after one dose reduction, the patient must be removed from protocol therapy.

6.2.3 Patients who have a dose-limiting non-hematological toxicity that does not resolve to Grade  $\leq 2$  or eligibility within 43 days after the start of the cycle, must be removed from protocol therapy.

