## 10.0 CRITERIA FOR REMOVAL FROM PROTOCOL THERAPY AND OFF STUDY CRITERIA

### 10.1 Criteria for Removal from Protocol Therapy

- a) Treatment failure (See [Appendix VIII](#) for definitions).
- b) Adverse Events requiring removal from protocol therapy (See [Section 6.1](#), [Section 6.2](#), and [Section 6.3.1](#))
- c) Refusal of protocol therapy by patient/parent/guardian
- d) Non-compliance that in the opinion of the investigator does not allow for ongoing participation.
- e) Completion of up to 2 cycles of therapy.
- f) Physician determines removal from protocol is in the patient's best interest.
- g) Repeat eligibility studies are outside the parameters required for eligibility prior to the start of GMI-1271 (Uproleselan) (See [Section 8.1](#)).
- h) Study is terminated by Sponsor.
- i) Pregnancy
- j) Development of secondary malignancy
- k) Patient receives concurrent cancer therapy that is not part of protocol therapy (See [Section 7.1](#))

**Patients who are removed from protocol therapy during Cycle 1 should continue to have the required observations in [Section 8.1](#) until the originally planned end of the cycle or until all adverse events have resolved per [Section 13.5](#) whichever happens LATER. The only exception is with documentation of the patient's withdrawal of consent. Patients who are removed from protocol therapy in subsequent cycles should have the necessary observations to ensure adequate clinical care.**

Patients who are off protocol therapy are to be followed until they meet the criteria for Off Study ([see below](#)). Ongoing adverse events, or adverse events that emerge after the patient is removed from protocol therapy, but within 30 days of the last dose of investigational agent, must be followed and reported via RAVE and CTEP-AERS (if applicable). Follow-up data will be required unless consent is withdrawn.

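### The delay-based DLT in 5.5.1.2 cannot be scored in patients who never receive Cycle 2, so it can only err toward too few DLTs

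*Combined protocol and SAP*

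**What the plan says.** Section 5.5 sets the window: "The DLT observation period will be the first cycle of therapy". Section 5.6 gives its length: "A cycle of therapy is considered to be 28 days".

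Section 5.5.1 has two non-hematological routes to a DLT.

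- 5.5.1.1 is the default: "Any Grade 3 or greater non-hematological toxicity attributable to protocol therapy with the specific exclusion of" a list of Grade 3 events. Fever, infection, sepsis, rash and mucositis are on that list with no limit on duration.
- 5.5.1.2 is the delay route: "Non-hematological toxicity that causes a delay of" 14 days or more between cycles.

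Cycle 2 is not guaranteed. The note under Table 1 allows it "if there is evidence of clinical benefit in the opinion of the treating physician" and if organ-function criteria are met. Section 5.2 asks for at least stable disease and renewed eligibility. Section 10.1 lets patients leave through refusal or physician decision.

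Under 11.2.1 a patient is evaluable for DLT after at least 85% of the prescribed Cycle 1 dose and the required toxicity monitoring. Receipt of Cycle 2 is not a condition. Section 11.3 accepts a dose level if at most 1 evaluable patient has a Cycle 1 DLT, with up to six enrolled. No section says how 5.5.1.2 is scored when Cycle 2 is not given.

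**The concern.** The delay item is the only way in which a prolonged Grade 2 event, or a prolonged Grade 3 event from the exclusion list, becomes a DLT. It works by observing a gap between two cycles. Without a second cycle there is no gap, so the literal score is no DLT, while the patient still counts in the denominator.

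Two patients with the same unresolved toxicity can therefore be scored differently because of leukemia status, family choice or physician judgment. The awkward case is the patient in whom the toxicity itself leads to the decision against Cycle 2: that patient scores no DLT on this item, while one who recovers enough for a late Cycle 2 scores one.

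The DLT count drives the primary dose decision. With a cut between 1 and 2 events in six patients, one missed event can turn de-escalation into acceptance. The same count feeds the combined Part A and Part B check in 11.3.

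**Working it through.** **Plan figures.** The plan states no DLT-rate assumption and no operating characteristics for its rule. Its planning totals reproduce: (6 + 6 + 6) × 1.2 = 21.6, so 22; and (12 + 12 + 6) × 1.2 = 36. This point changes neither.

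**Which events are affected.** Grade 3 or higher attributable events outside the exclusion list are DLTs under 5.5.1.1 whether or not Cycle 2 follows. What is exposed is Grade 2 or lower toxicity, and listed Grade 3 events, lasting long enough to hold up Cycle 2 by 14 days.

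**Calendar.**

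- Scheduled start of Cycle 2: 28 + 1 = Day 29.
- Delay of 14 days reached: 29 + 14 = Day 43, after the 28-day cycle named as the DLT period.
- Off-study criterion 10.2(a), 30 days after the last uproleselan dose: 8 + 30 = Day 38.
- Hematological DLT (5.5.2.1), 43 days after the first fludarabine/cytarabine day: 2 + 43 = Day 45.

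The hematological DLT is thus read on a fixed date that does not need a Cycle 2. The delay item has none.

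**Direction.** A missed event can only remove a DLT, so this item can only lower the count.

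**Size.** Let p be the DLT rate if every evaluable patient could be scored, b the proportion of patients whose only DLT comes through 5.5.1.2, and q the share of those patients who get no Cycle 2.

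- Scored rate: p′ = p − b·q
- Chance of passing: P(≤1 of 6) = (1 − p′)^6 + 6p′(1 − p′)^5

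At p = 1/3 with nothing lost: 64/729 + 192/729 = 0.351. This rate already fails the 11.2.2 requirement of fewer than one-third, so passing is a wrong decision. All b and q values below are assumptions.

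| b | q | Scored rate (p = 1/3) | P(pass), p = 1/3 | Change | P(pass), p = 0.40 (0.233 if all scored) |
|---|---|---|---|---|---|
| 0.01 | 0.25 | 0.331 | 0.356 | +0.5 points | 0.237 |
| 0.02 | 0.50 | 0.323 | 0.371 | +2.0 points | 0.249 |
| 0.05 | 0.50 | 0.308 | 0.402 | +5.1 points | 0.274 |
| 0.10 | 0.75 | 0.258 | 0.514 | +16.3 points | 0.368 |

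If q is taken as the share without Cycle 2 among all patients, the table assumes that these toxicities do not themselves make Cycle 2 less likely. If they do, q is higher. At the ceiling of q = 1 and p = 1/3, the change is +2.0 points for b = 0.01 and +22.3 points for b = 0.10.

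**The case against.** **The gap may be small and handled in practice.** Most serious toxicity is caught by 5.5.1.1. Under 14.5.2 the study chair scores DLTs and a weekly call reviews them, so a sensible reviewer might treat a toxicity that prevents Cycle 2 as a DLT. Both points are fair: the first limits the size, and the second may rescue individual cases. Neither supplies a rule, and a literal reader would score no DLT.

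**A reader might infer that the liver-enzyme exclusion has the same downward bias.** It is tied to recovery "prior to the time for the next treatment cycle". The documents do not support that inference. An exclusion that is not met leaves the event a DLT, so if it could not be met without a next cycle the bias would be upward. With an assumed 5% of such events and half of those patients without Cycle 2, the scored rate would rise from 0.333 to 0.358 and P(pass) would fall from 0.351 to 0.304. The phrase can also be read as the scheduled date. ALT is due weekly in Cycle 1, and the therapy delivery map puts ALT and AST on Day 28 for all patients. On that reading there is no bias for these enzymes.

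**A reader might take non-remission as the share without Cycle 2.** The background rates leave 100 − 65.8 = 34.2% to 100 − 41 = 59% without remission. But 5.2 asks only for stable disease, Appendix VIII judges treatment failure after up to two cycles, and the 59% FLAG remission rate was itself reached after two cycles. These figures do not show who stops after one.

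**Larger shifts can be constructed, but they may not be wrong decisions.** Assume 10% other DLTs and 20% delay-type toxicity. The fully scored rate is 1 − 0.9 × 0.8 = 28%, and P(pass) is 0.464. If 60% or 40% have a Cycle 2, it becomes 0.636 or 0.724. Since 28% is below one-third, the dose meets the plan's own definition, and these numbers do not show an over-toxic dose being accepted.

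**Conclusion.** The point holds for 5.5.1.2 only. As written, the item cannot be met in a patient without Cycle 2, that patient remains in the denominator, and the resulting error in the DLT count can only be downward.

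The size is not known. Over the assumed values tabulated, the chance of wrongly passing a dose with a true DLT rate of 1/3 rises by 0.5 to 16 points. The lower half of that range is modest, and the upper end needs one patient in ten to have a DLT of this kind alone. The case for change rests on the scoring rule being undefined for a foreseeable group of patients, not on any one of these figures. No bias is established for the liver-enzyme exclusion; its date needs defining and nothing more.

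**What to change.** Keep the plan's own 14-day threshold, but read it on a fixed date in every DLT-evaluable patient. Add to 5.5.1.2, for example:

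*or, in a patient who does not receive Cycle 2 for any reason, attributable non-hematological toxicity that would by itself still have prevented starting Cycle 2 under Section 5.2 at 14 days after its scheduled start (about Day 43).*

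Four points go with it.

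- Do not borrow the resolution level in 6.2.3, which says that patients not recovered "within 43 days after the start of the cycle, must be removed from protocol therapy". Its level is Grade 2 or lower, or eligibility, so a persistent Grade 2 event would still never count. It also governs toxicity that is already dose-limiting.
- Reconcile follow-up so that Day 43 is observed. Section 10.1 continues observation "until the originally planned end of the cycle or until all adverse events have resolved", but for patients removed during Cycle 1. Someone who completes Cycle 1 and then stops is not clearly covered, and can meet 10.2(a) at about Day 38. State also how a patient who dies of leukemia or starts other therapy before Day 43 is scored.
- Reconcile the Cycle 2 start conditions that the new test relies on: 5.2 points to all of Section 4.0, while the note under Table 1 names only organ function.
- Define the time for the next cycle in the liver-enzyme exclusion as the scheduled calendar day.

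The cost is a possibly slightly higher observed DLT rate and follow-up to about Day 43, which the hematological DLT already requires. The planned 22 and maximum 36 patients are unchanged.
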